### 14.3 Laboratory Test Abnormalities

In addition to being recorded on the appropriate laboratory test results CRF, or being electronically submitted from a central laboratory, any clinically significant laboratory test result that meets the criteria for an AE (see [Section 14](#)) or SAE (see [Section 14.2](#)) must also be recorded on the AE CRF. SAEs must be reported to the Sponsor and IRB as per [Section 14.2](#). In these cases, TI will typically require additional information about the clinically significant abnormality, including information regarding relationship to test article or other causes, any action taken, and resolution. Other laboratory test abnormalities will be addressed by the investigator on the actual laboratory test reports, and on the associated laboratory test results CRF.

### 14.4 Pregnancy

WOCBP include any female who has experienced menarche or is 10 years of age or older and who has not undergone successful surgical sterilization (hysterectomy, bilateral tubal ligation, or bilateral oophorectomy) or is not postmenopausal [defined as amenorrhea >12 consecutive months in women 50 years of age and older]. Even women who are using hormonal methods of contraception and/or barrier methods to prevent pregnancy, practicing abstinence, or who have a monogamous partner that is sterile (e.g., vasectomy) should be considered to be of childbearing potential. Surgical means of sterilization (e.g., vasectomy, tubal ligation) must be a minimum of six months post-procedure to be considered effective birth control.

WOCBP must have a negative pregnancy test prior to study enrollment and must use the methods of contraception outlined in the protocol during the course of the study, in a manner such that risk of failure is minimized. Methods of acceptable contraception include A) total abstinence OR B) two forms of birth control including:

- Oral, patch, injected, or implanted hormonal methods of contraception AND
- Partner vasectomy (performed at least six months prior to study entry) OR barrier

---

 WOCBP taking hormonal therapy must be on treatment for (1) oral or patch: one complete cycle (e.g., four to eight weeks) or (2) injectable or implanted: at least one week prior to study entry, continued per label, and must not change their dosing regimen during the study.

methods of contraception (barrier methods include male condom with or without spermicide, diaphragm with spermicide, or cervical cap with spermicide) OR vaginal contraceptive sponge containing a spermicide.

Prior to study enrollment, WOCBP must be advised of the importance of avoiding pregnancy during study participation and the potential risk factors for an unintentional pregnancy. The subject must sign an informed consent/assent form documenting this discussion.

WOCBP should be instructed to contact the investigator immediately if they suspect they might be pregnant (e.g., missed or late menstrual period). If a subject or investigator suspects that a subject may be pregnant at any time during the study the test article must be withheld until the results of laboratory pregnancy testing are available. If pregnancy is confirmed, the subject must not receive or apply further test article and must be discontinued from the study. The investigator must immediately notify the Medical Monitor of the pregnancy and record the pregnancy on the appropriate pregnancy surveillance form.

If following initiation of study treatment, it is subsequently discovered that a study subject was pregnant or may have been pregnant at the time of test article exposure, the investigator must immediately notify the Medical Monitor of this event, and record the pregnancy on the appropriate pregnancy surveillance form. The form will be sent to TI. The investigator must notify the IRB of any pregnancy associated with the study therapy and keep careful source documentation of the event.

Protocol-required procedures for those subjects that are discontinued from the study must be performed on the subject unless contraindicated by pregnancy (e.g., x-ray studies). Other appropriate pregnancy follow-up procedures should be considered if indicated, including counseling of the subject by the investigator and her managing physician or health care provider (e.g., obstetrician). In addition, the investigator must report to TI, on the appropriate TI pregnancy surveillance form(s), any follow-up information regarding the course of the pregnancy, including perinatal and neonatal outcome. Although pregnancy itself is not an AE, any complications during pregnancy should be recorded as AEs (or SAEs, if they fulfill the SAE criteria). Offspring should be followed for a minimum of eight weeks. Any congenital anomaly/birth defect in a child born to a subject exposed to the test article(s) should be recorded as a SAE and details documented in the pregnancy surveillance form. Abortion, whether accidental, therapeutic or spontaneous should be reported as a SAE.

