Treatment Groups	
There will be two parts to this study. In Part 1, subjects will be randomized to two treatment groups and treated bilaterally with active and vehicle test articles (as described below) for eight weeks. In Part 2, subjects will enter an active only follow-up period of four weeks in which both Treatment Areas identified in Part 1 will be treated with the active test article of their assigned Treatment Group.
 
After enrollment in the study, each subject will be randomized (1:1) to one of two Treatment Groups. Randomization will be stratified by CI subtype. Each subject will have two comparable Treatment Areas defined per protocol. One Treatment Area shall be randomly designated to be treated with one “active” test article with the contralateral Treatment Area assigned to the second test article (i.e., vehicle) within the assigned Treatment Group for Part 1. In Part 2, both Treatment Areas will be treated with the “active” test article within the assigned Treatment Group.
 
Treatment Groups Blinded Test Articles:
 
 
• Group 1: PAT-001, 0.1% vs vehicle
 
• Group 2: PAT-001, 0.2% vs vehicle
 
 
Treatments will be applied twice daily to all disease affected skin in the Treatment Area. Dosing may be adjusted by the investigator if there are concerns with tolerability as detailed in the protocol.
 
Subjects will have the option of participating in the pharmacokinetic (PK)

	portion of the study per the Schedule of Events.
Duration of Treatment	Twice a day application for 12 weeks: eight weeks in Part 1 and an additional four weeks in Part 2.
Duration of Study	Each subject will participate in the study for approximately 18 weeks (including up to 45-day screening period).
Study Population	Male and/or female subjects, 12 years of age and older with confirmed diagnosis of protocol specified subtypes of CI.
Total Number of Subjects	Approximately 18 subjects will be enrolled in the study, with approximately nine subjects randomized to each Treatment Group.
Number of Sites	Approximately three sites will participate in the study.

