#### 5.1.1 Inclusion Criteria

1. Subject is male or non-pregnant female, 12 years of age and older. Females must be post-menopausal, surgically sterile, or use two forms of birth control. Women of childbearing potential (WOCBP) must have a negative urine pregnancy test (UPT) at Visit 1/Screening and Visit 2/Baseline.
2. Subject has provided written informed consent/assent. A subject under 18 years of age must provide written informed assent and be accompanied by the parent or legal guardian at the time of assent/consent signing. The parent or legal guardian must provide informed consent for the subject. If a subject becomes 18 years of age during the study the subject must provide written informed consent at that time to continue study participation.
3. Subject is willing and able to apply the test article(s) as directed, comply with study instructions, and commit to all follow-up visits for the duration of the study.
4. Subject has a clinical diagnosis of either Lamellar (e.g., transglutaminase 1-deficient) or X-Linked (e.g., deletion of steroid sulfatase gene) subtypes of CI and agrees to

---

 Defined as amenorrhea greater than 12 consecutive months in women 50 years of age and older.

 Hysterectomy, bilateral tubal ligation (at least six months prior to initiation of treatment), or bilateral oophorectomy.

 Methods of acceptable contraception include A) total abstinence OR B) two forms of birth control including:

- 1) oral, patch, injected, or implanted hormonal methods of contraception, AND
- 2) a) partner vasectomy (performed at least six months prior to study entry) OR b) barrier methods of contraception [barrier methods include male condom with or without spermicide, diaphragm or cervical cap – both of which are to be used with spermicide] OR c) a vaginal contraceptive sponge containing a spermicide.

Subjects who become sexually active or begin to have relations with a partner during the study must agree to use two forms of birth control for 30 days prior to having relations and to continue such forms for the duration of the study.

 WOCBP taking hormonal therapy must be on treatment for (1) oral or patch: one complete cycle (e.g., four to eight weeks) or (2) injectable or implanted: at least one week prior to study entry, continued per label, and must not change their dosing regimen during the study.

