 UPTs must have a minimum sensitivity of 25 mIU  $\beta$ -hCG/mL.

- genetic testing to confirm such diagnosis during the study.
5. Subject must have two contralateral comparable Treatment Areas, as defined per protocol. Each Treatment Area must have a minimum of 150 cm^2 of affected diseased skin as identified by the investigator. [Note: each Treatment Area shall be contained within a discrete anatomic unit as defined in the protocol and shall not exceed 6% BSA, excluding palms and soles.]
  6. Both Treatment Area(s) must be of comparable size per protocol and have an identical IGA score, with a score of either 3 (moderate) or 4 (severe) at Visit 2/Baseline.
  7. Subject is either naïve to oral retinoid treatments; or, if subject is currently taking retinoids, has completed at-least a 12-week washout of oral retinoids or a 2-week washout of topical retinoids prior to Visit 2/Baseline.
  8. All protocol specified hematology, chemistry, and urinalysis assessments are considered not clinically significant with respect to the subject's participation in the study and typically are  $\leq 2.5$  times upper limit of normal (ULN) at Visit 1/Screening.
  9. Subject has not donated blood within 30 days of Visit 2/Baseline and agrees to not donate blood during study drug treatment and for one month following discontinuation of treatment.
  10. Subject is in good general health and free of any disease state or physical condition that might impair evaluation of the Treatment Areas or which, in the investigator's opinion, exposes the subject to an unacceptable risk by study participation.

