### **5.1.2 Exclusion Criteria**

1. Subject is pregnant, lactating, or is planning to become pregnant during the study.
2. Subject has inflammatory skin disease unrelated to ichthyosis.
3. Subject has previously failed on topical / oral retinoid therapy for treatment of CI.
4. Subject has used topical retinoid-containing therapies to treat Treatment Areas (except emollients) within two weeks prior to Visit 2/Baseline or topical corticosteroids within five days prior to Visit 2/Baseline. Non-Treatment Areas can be treated with topical therapies including emollients, keratolytics, or sunscreen.
5. Subject has used ultraviolet (UV) treatment for ichthyosis within four weeks prior to Visit 2/Baseline.
6. Subject has undergone systemic therapies using Vitamin A supplements or St. John's Wort within four weeks prior to Visit 2/Baseline. Note: Use of systemic retinoids is prohibited within 12 weeks of Visit 2/Baseline per inclusion criterion #7.
7. Subject is immunosuppressed (e.g., HIV, systemic malignancy, graft host disease, etc.).
8. Subject is currently taking concomitant immunosuppressive drugs, including systemic corticosteroids within two weeks of Visit 2/Baseline.
9. Subject has untreated secondary infections; however, subject may become eligible after successful treatment of his/her infections at the investigator's discretion.
10. Subject has clinically significant metabolic, pulmonary, cardiac, hematologic, renal, hepatic, immune, neurologic, psychiatric, infectious, neoplastic, or malignant disease

---

 Fluorescence in situ hybridization (FISH) positive confirmation of steroid sulfatase gene deletion is also acceptable to diagnose X-Linked subtype of CI.

- (other than non-melanoma skin cancer) that would preclude his/her participation in the study.
11. [For PK Subjects Only] Subject has chronic gastrointestinal disease such as Crohn's disease, irritable bowel syndrome, colitis, inflammatory bowel disease, or chronic diarrhea.
  12. Subject with a history of drug or alcohol abuse within the past six months.
  13. Subject is currently enrolled in an investigational drug or device study.
  14. Subject has used an investigational drug or investigational device treatment within 30 days prior to Visit 2/Baseline.
  15. Subject has a history of allergy to any of the ingredients in the test articles (see [Section 6.1](#)).

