### 6.3 Warnings, Precautions and Contraindications

These test articles are for topical use only. Care should be taken to avoid contact with eyes and all mucous membranes. If contact with eyes occurs, rinse thoroughly with water.

Subjects with a known allergy to any of the ingredients in the test articles should not participate in this study.

Should severe skin irritation or rash develop, the subject should contact the investigator immediately to discuss the possibility of dose modifications or moisturizer use as detailed in [Section 6.2](#)).

In case of accidental ingestion, subjects should contact the investigator immediately.

The effects of the test article in nursing mothers, pregnant women and their unborn children are unknown. WOCBP must not be pregnant, lactating, or planning a pregnancy during the study period.

Exposure to sunlight, including UV sunlamps, may provoke additional irritation. Therefore, exposure should be avoided or minimized during the use of the test articles. In cases where significant exposure to sunlight cannot be avoided, use of sun protection

---

 DML Lotion will be provided to subjects. Other bland emollients (e.g., Lubriderm [without alpha hydroxy acid], or other moisturizers that do not contain any “active” ingredients [e.g., salicylic acid, lactic acid, pyruvic acid, urea, or any other ingredient that could irritate or cause a keratolytic effect]) may be used with approval from the investigator, but must be documented as a concomitant medication/therapy.

measures such as sunscreen products (for areas outside of the Treatment Area) and/or protective clothing over the Treatment Areas is recommended.

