### **9.7 Visit 9 (Day 84 $\pm$ 4): End of Study and Early Termination**

*At this visit the investigator or designee will:*

- Query the subject about any changes in health status since the previous visit, including concomitant medications and therapies, and document the findings.
- Perform brief physical exam. Record any new or worsening findings as AEs.
- Perform vital signs (heart rate, respiration rate, blood pressure, and temperature).
- Perform UPT for WOCBP.
- Collect urine and blood samples for clinical laboratory tests. If possible, subject will have fasted for approximately eight hours or more prior to these laboratory tests.
- Perform IGA for each Treatment Area.
- Assess CI Signs/Symptoms for each Treatment Area.
- Document LSRs for each Treatment Area.
- Take photographs.
- Document test article accountability; weigh the tubes and collect all test articles.
- Collect Subject Diary.
- Exit the subject from the study.

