#### **13.1 Completion of the Study**

Subjects who complete the 12 week course of treatment as specified in this protocol and all of the Visit 9/Day 84 evaluations will have completed the study.

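### For subjects who complete treatment, required contraception and the bar on planning pregnancy end at Visit 9, about 4 to 20 hours after the last active application

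*Combined protocol and SAP*

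**What the plan says.** **Contraception.** Section 14.4 states that women of childbearing potential "must use the methods of contraception outlined in the protocol during the course of the study". Inclusion criterion 1 requires two forms of birth control but gives no end date. Footnote 24 (footnote 3 in the synopsis) tells subjects who become sexually active during the trial "to continue such forms for the duration of the study".

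**Planning a pregnancy.** Exclusion 1 reads "Subject is pregnant, lactating, or is planning to become pregnant during the study". Section 6.3 adds that "WOCBP must not be pregnant, lactating, or planning a pregnancy during the study period".

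**End of participation.** The last step of Section 9.7, at Visit 9 (Day 84±4), is "Exit the subject from the study". Section 13.1 defines completers as "Subjects who complete the 12 week course of treatment as specified in this protocol and all of the Visit 9/Day 84 evaluations". The Schedule of Events shows nothing after Visit 9.

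**Rules that run longer.** Under inclusion criterion 9 the subject "agrees to not donate blood during study drug treatment and for one month following discontinuation of treatment". Item (v) of the reportable list in Section 14.2 covers pregnancies confirmed up to one month after leaving the study. The same section asks for serious adverse events within 30 days of stopping.

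**The concern.** Visit 9 is both the end of treatment and the end of the study. A rule that lasts as long as the study therefore stops when treatment stops. In Part 2 both Treatment Areas receive active ointment, so every completer leaves on active drug, whichever side had vehicle in Part 1.

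The protocol treats the hazard as real in principle. Section 1 names teratogenicity as one of the most serious potential adverse effects of isotretinoin. Section 14.1 keeps it as a potential risk until there is experience with the ointment. Section 6.3 says the effects on pregnant women and unborn children are not known. Yet under the protocol text a woman may stop contraception, or try to conceive, on the day she exits. The provisions that do run past exit concern blood donation and the reporting of events, and none of them prevents conception. What is at stake is subject protection. No endpoint or analysis depends on it.

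**Working it through.** The plan states no post-treatment contraception interval, so there is no figure to reproduce. The check asks how much time the stated rule leaves and compares it with the stated half-life.

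**Inputs**
- Elimination half-life of isotretinoin: 10 to 20 h (Section 2).
- Shortest gap from last application to a clinic visit: 4 h (Section 6.2).
- Gap for subjects in the optional PK portion: 12 h ± 30 min (Section 6.2; synopsis, Visit 9).
- Longest gap considered: 20 h. This is an assumption. Section 9.2 tells subjects to hold dosing on visit days, so someone who doses in the evening and attends in the afternoon could reach about 20 h.
- Five half-lives as the yardstick: a reviewer's convention that appears nowhere in the protocol.

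**Time needed**
- 5 × 10 h = 50 h = 2.1 days
- 5 × 20 h = 100 h = 4.2 days

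**Time given, in half-lives**
- Smallest: 4 / 20 = 0.2
- Largest: 20 / 10 = 2.0

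**Shortfall (five half-lives minus gap)**

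| Gap | Half-life 10 h | Half-life 20 h |
|---|---|---|
| 4 h | 46 h (1.9 days) | 96 h (4.0 days) |
| 12 h | 38 h (1.6 days) | 88 h (3.7 days) |
| 20 h (assumed) | 30 h (1.3 days) | 80 h (3.3 days) |
| 24 h (sensitivity) | 26 h (1.1 days) | 76 h (3.2 days) |

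The shortfall is 1.3 to 4.0 days over gaps of 4 to 20 h. It does not close at 24 h.

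**Is there follow-up hidden in the study duration?** The synopsis puts participation at about 18 weeks, screening included. Screening of up to 45 days plus 84 days is 129 days, or 18.4 weeks, against 18 × 7 = 126 days. Nothing is left over.

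**How many subjects?** Section 7 requires at least 12 of 18 subjects to have the X-linked subtype, so at most 18 − 12 = 6 have the lamellar subtype. If all X-linked subjects are male (an assumption; Section 1 gives the frequency of that subtype in males), the number affected is between 0 and about 6 (6/18 = 33%). If half of six lamellar subjects were women of childbearing potential, it would be 3 (3/18 = 17%).

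**Early terminators.** Section 13.2 asks for a return at the next scheduled visit. Nominal spacing between clinic visits is 7, 7, 14, 28 and 27 days, so these subjects may have from 0 to about 28 days of incidental cover. The calculation above is for completers.

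**The case against.** **Exposure is expected to be low.** Section 14.1 says so and regards many of the systemic risks as unlikely. Section 1 notes that isotretinoin also occurs naturally in cells. This limits the practical risk, and it stands. It remains an expectation: Section 14.1 reports no human studies of the ointment, and measuring plasma levels is one of this trial's secondary objectives.

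**The short half-life was considered.** Section 2 links it to simpler family planning. That makes the omission look more like a judgement than an oversight, but no interval was drawn from it.

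**Some safeguards exist.** There is a pregnancy test at Visit 9. Section 14.4 asks women to contact the investigator if they suspect pregnancy, and notification runs one month past exit. These detect or report a pregnancy but do not prevent one.

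**Other text may say more.** Section 14.4 has the pregnancy discussion documented in the signed consent or assent. Those pages and most of the subject instruction sheets were not available, so the point is confined to the protocol text.

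**Stronger readings that the documents do not support**
- A reader might infer that cover ends at most 12 hours after dosing. The 12-hour rule applies to PK subjects only.
- A reader might take footnote 24 as an end date for all women. It covers only those who become sexually active during the trial. Section 14.4 sets the general rule.
- A reader might convert the gap into drug remaining (with first-order decay, 2^−0.2 = 87% down to 2^−2 = 25%) and treat that as risk. It is a share of an unmeasured level that may be small.
- A reader might think that half-life demands a month. Five half-lives are 2.1 to 4.2 days, and the protocol gives no reason for its blood-donation month.

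**Conclusion.** The point holds for completers, as a minor safety improvement. The stated rules end at Visit 9, about 4 to 20 hours after the last active application. That is 0.2 to 2 half-lives, and 1.3 to 4.0 days short of five. No protocol text available for review extends either rule.

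The size rests on the half-life quoted in Section 2, which was not measured for this ointment; on the assumed 20-hour upper gap; and on five half-lives as a convention. Further uptake from skin is ignored, and no half-life is given for tretinoin. At most about 6 of 18 subjects are affected, if all X-linked subjects are male.

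A reader might infer that the trial exposes women to a demonstrated fetal hazard. The documents do not show that: exposure is expected to be low, and no data in them link residual topical drug in the days after stopping to harm. The case for acting is that the possible harm is serious and the correction cheap.

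**What to change.** In inclusion criterion 1 and its contraception footnotes (3 and 4 in the synopsis, 24 and 25 in Section 5.1.1), exclusion 1, Section 6.3 and Section 14.4, require contraception, and no planning of pregnancy, until one month after the last application. Present the month as chosen for consistency with inclusion criterion 9 and with item (v) of Section 14.2, not as a pharmacokinetic result. In Section 9.7, which covers Visit 9 and early termination, add a reminder to continue contraception for that month and to contact the site if pregnancy is suspected. Item (v) needs no change.

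The cost is an amendment with IRB approval and, where the IRB requires new consent or assent wording, signatures from subjects already enrolled (Section 18.4). The burden on subjects is about one more month of contraception for 0 to about 6 of them. No visit or test is added.
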